Describe methods used to protect the privacy of subjects and maintain confidentiality of data collected. This typically includes such practices as substituting codes for names and/or medical record numbers; removing face sheets or other identifiers from completed surveys/questionnaires; proper disposal of printed computer data; limited access to study data; use of password-protected computer databases; training for research staff on the importance of confidentiality of data, and storing research records in a secure location.

NOTE: Additional measures, such as obtaining a Certificate of Confidentiality, should be considered and are strongly encouraged when the research involves the collection of sensitive data, such as sexual, criminal or illegal behaviors.

Data collected via REDCap are secured and stored behind the Partners firewall and follow Partners Healthcare Information Security policies for authenticated, minimum access. Data collected via regular mail will be scanned and stored electronically in our secure, access-limited, password-protected research folder on the Partners shared drive, same as data that are collected via e-mail. Original copies of data collected via regular mail will then be disposed in the HIPAA-compliant bins at Massachusetts General Hospital.

SENDING SPECIMENS/DATA TO RESEARCH COLLABORATORS OUTSIDE PARTNERS

Specimens or data collected by Partners investigators will be sent to research collaborators outside Partners, indicate to whom specimens/data will be sent, what information will be sent, and whether the specimens/data will contain identifiers that could be used by the outside collaborators to link the specimens/data to individual subjects.

Not applicable

Specifically address whether specimens/data will be stored at collaborating sites outside Partners for future use not described in the protocol. Include whether subjects can withdraw

their specimens/data, and how they would do so. When appropriate, submit documentation of IRB approval from the recipient institution.

Not applicable

RECEIVING SPECIMENS/DATA FROM RESEARCH COLLABORATORS OUTSIDE PARTNERS

When specimens or data collected by research collaborators outside Partners will be sent to Partners investigators, indicate from where the specimens/data will be obtained and whether the specimens/data will contain identifiers that could be used by Partners investigators to link the specimens/data to individual subjects. When appropriate, submit documentation of IRB approval and a copy of the IRB-approved consent form from the institution where the specimens/data were collected.

Not applicable

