American Indian/Alaska Native	1	1	2
Asian	5	5	10
Black/African-American	13	13	26
Hawaiian/Pacific Islander	1	0	1
White	73	71	144
Multirace	3	3	6
Other race	6	5	11
Ethnicity	Male (N)	Female (N)	Total (N)
Hispanic (Latino/Latina)	16	16	32
Non-Hispanic	83	85	168

Briefly describe study procedures. Include any local site restrictions, for example, “Subjects enrolled at Partners will not participate in the pharmacokinetic portion of the study.” Describe study endpoints.

Potential eligible participants will be directed to our study recruitment website (www.downsyndromeclinictoyou.com) to complete the eligibility screening questionnaire (Appendix A). Information of frequently asked questions and answers will also be provided on our study recruitment website (Appendix B). After a questionnaire is submitted and a parent/caregiver is deemed eligible, our study personnel will send an email notification containing a unique link to our online consent form in REDCap (Appendix C). Once they have provided consent, the parent/caregiver will continue on to complete the baseline assessment. Our study personnel will then be notified by e-mail, after which we will randomize the participant 1:1 to either the Intervention or Control arm (Appendix D).

To limit chance confounding between variables that might influence guideline compliance, we will stratify randomization based on two variables (six strata) collected prior to randomization during the Baseline assessment when data are gathered only from parents (PCPs are first surveyed after their appointment with the patient who has Down syndrome):

- Travel time to primary care physician: < 30 minutes; 30–60 minutes; > 60 minutes
- Primary insurance: public (e.g., Medicaid, Medicare) or private

Given the sequence of study procedures, we will not stratify on any variables reported by the PCP. With 200 participants randomized, we expect to

achieve effective mixing of PCP characteristics that might be associated with differential guideline compliance. Moreover, by not conditioning on PCP characteristics, findings from our primary analysis will be most broadly generalizable. However, we do want to increase precision in our secondary analyses by accounting for relevant sources of variation among PCP practices. To this extent, we will collect the following variables for inclusion as covariates:

- PCP practice size: < 5 MDs; 5–9 MDs; 10+ MDs (collected in PCP Experience Survey during Post-visit Assessment 1)

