- PCP practicing in a federally qualified community health center: yes or no (collected in PCP Experience Survey during Post-visit Assessment 1)
- Years of PCP practice (collected in PCP Experience Survey during Post-visit Assessment 1)
- Number of patients with Down syndrome cared for by PCP (collected in PCP Experience Survey during Post-visit Assessment 1)

Baseline Assessment (Intervention & Control Arms)

The intervention and control groups will both complete a Baseline Assessment; up to 3 e-mail reminders will be sent to the parent/caregiver every 1 week. The Baseline Assessment, implemented using REDCap (Research Electronic Data Capture), a secure, NIH-funded, and Health Insurance Portability and Accountability Act (HIPAA) compliant web-based application hosted by Partners HealthCare Research Computing, will request the following information:

- *Caregiver information*: first name, last name, gender, date of birth, relationship to patient, phone number, address, and email address
- *Child or dependent's information*: first name, last name, gender, date of birth, race/ethnicity (NIH standardized format)
- *PCP information*: first name, last name, gender, office phone, office address and e-mail (if available)
- Travel time to primary care physician: < 30 minutes; 30–60 minutes; > 60 minutes
- Primary insurance: public (e.g., Medicaid, Medicare) or private
- *Date of annual well visit ("PCP visit") appointment*
- *Symptoms indicating need for celiac disease testing or sleep study*. We plan to assess these symptoms among other symptoms not related to these conditions so as to minimize any priming effects. For example, "Does your child snore at night?" might be asked next to "Does your child have any rashes?" (A sleep study might be warranted for snoring, but not for rashes.) ([Appendix E](#))
- *Health Care Outcome Survey* (Metrics measuring adherence to national health care guidelines): thyroid screening, celiac disease screening, sleep apnea testing, ophthalmology exams, and audiograms ([Appendix F](#))

- *Secondary outcome measures:* PedsQL 2.0 Family Impact Module and PedsQL 4.0 parent-proxy, standard Short Form 15 Generic Core Scales (Appendix G)

Intervention Arm

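### Four PCP covariates meant to sharpen the secondary analyses exist only when the PCP returns a post-visit survey; limiting the adjusted models to responders could lose the precision sought

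*Combined protocol and SAP*

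**What the plan says.** Under Research Design and Methods, randomisation is stratified on travel time and primary insurance, described as "two variables (six strata) collected prior to randomization during the Baseline assessment when data are gathered only from parents". PCP characteristics are left out of the stratification because "PCPs are first surveyed after their appointment with the patient who has Down syndrome". The plan expects randomisation of 200 participants to "achieve effective mixing of PCP characteristics that might be associated with differential guideline compliance", and it keeps the primary analysis free of them on the ground that "by not conditioning on PCP characteristics, findings from our primary analysis will be most broadly generalizable".

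For the secondary analyses it takes a different line: "we do want to increase precision in our secondary analyses by accounting for relevant sources of variation among PCP practices", and to this end "we will collect the following variables for inclusion as covariates". Four follow: practice size in three bands, whether the practice is a federally qualified community health center, years in practice, and the PCP's experience with the condition. Each carries the same source note; the last reads "Number of patients with Down syndrome cared for by PCP (collected in PCP Experience Survey during Post-visit Assessment 1").

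The Baseline Assessment asks caregivers only for the PCP's name, gender and contact details, so no second source is planned. Survey Implementation supports reply with mail, electronic and e-mail routes, three reminders and a closing phone call, and Recruitment Procedures adds a $40 payment. Survey Implementation acknowledges PCP non-response but answers it only for the primary outcomes.

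The Data Analysis Plan specifies a repeated-measures ANOVA with a shared baseline for six PedsQL scores, each tested at 0.008 two-tailed. It mentions no PCP covariates, no stratification factors and no handling of missing values in that model.

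**The concern.** The aim is precision, but the chosen covariates can be observed only for participants whose PCP replies. When no rule is written, a usual default is to drop records with a missing covariate. The adjusted analysis then gains from variance explained and loses from a smaller sample, and the loss can easily be the larger of the two.

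The responder subset is also formed after randomisation. Under Intervention Arm, only intervention families obtain a Primary Care Provider Plan before the visit, so the arms could plausibly differ in which PCPs reply. A comparison within responders is no longer the comparison of everyone randomised.

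Finally, a reader cannot tell which secondary models are to carry the covariates. The covariate passage speaks of guideline compliance, while the only secondary models that are specified are for PedsQL and name no covariates. That leaves a choice open until after the data are seen.

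**Working it through.** The plan gives no PCP response rate, no variance explained and no figure for the precision expected, so there is nothing of its own to reproduce. What follows is a range under stated assumptions.

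**From the documents:** 200 participants, 1:1 allocation; four covariates using 5 degrees of freedom (practice size 2, health center status 1, years 1 if linear, number of patients 1 if linear).

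**Assumed:** complete-case fitting; r, the fraction of PCPs replying among participants with an observed outcome; R2, the share of outcome variance the covariates explain; reply unrelated to outcome.

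**Formula.** Ratio of the adjusted complete-case SE to the unadjusted SE in all participants with an observed outcome:

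- large sample: sqrt[(1 − R2)/r]; precision is lost when R2 < 1 − r
- allowing for 5 df, with up to 200 outcomes observed: sqrt[(1 − R2)/r × (200r − 3)/(200r − 8)]

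**Worked case, R2 = 0.10**

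- r = 0.7: sqrt(0.90/0.7 × 137/132) = 1.155
- r = 0.8: sqrt(0.90/0.8 × 157/152) = 1.078
- r = 0.9: sqrt(0.90/0.9 × 177/172) = 1.014
- r = 1.0: sqrt(0.90 × 197/192) = 0.961

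Without the df term the first three are 1.134, 1.061 and 1.000.

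**Range (with 5 df)**

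| r | R2 = 0.05 | R2 = 0.10 | R2 = 0.20 | Break-even R2 |
|---|---|---|---|---|
| 0.5 | 1.415 | 1.378 | 1.299 | 0.526 |
| 0.7 | 1.187 | 1.155 | 1.089 | 0.326 |
| 0.8 | 1.108 | 1.078 | 1.016 | 0.225 |
| 0.9 | 1.042 | 1.014 | 0.956 | 0.125 |

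Break-even R2 = 1 − r(200r − 8)/(200r − 3); for r = 0.7, 1 − 0.7 × 132/137 = 0.326.

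**Checks by simulation.** A linear model with 200 participants, five covariates and R2 = 0.10 (3,000 trials per setting) gave ratios of 1.24, 1.08 and 1.02 at 60%, 80% and 90% response. For the adherence count, a beta-binomial fit (2,000 trials per setting; assumed 45% control completion, 2 to 5 indicated tests, covariates explaining about 10% of the variance in proportion completed) gave equivalent SE ratios of about 1.12, 1.05 to 1.06, and 1.00 at 70%, 80% and 90%. The result is therefore much the same for either outcome.

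**Selection.** In a further simulation (3,000 trials, true effect 0.4 SD) complete-case bias was about zero when reply was 70% in both arms, or 60% v 80% but unrelated to outcome. It reached −0.04 or −0.08 SD only when reply was 60% v 80% and also driven by a trait correlated 0.3 or 0.5 with outcome. In those two settings imputation on all participants left −0.01 SD, and adjustment for a baseline variable alone left 0.00.

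**The case against.** The strongest reply is that the harm depends on a method the plan never states. Complete-case fitting, the response rate and R2 are all assumptions; at 90% response with R2 of 0.20 the complete-case fit still gains about 4%. That stands, and it is why the result is given as a condition and a range.

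Second, all comparisons against 200 ignore caregiver loss. If the caregivers who drop out tend to be those whose PCPs do not reply, overall PCP response overstates the loss. This also stands: the r that matters is response among participants with an observed outcome. Further, the PCP-experience outcome comes from the same survey as the covariates, so adjustment there costs little beyond item non-response.

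Third, imputation buys little precision. In the selection runs its relative SE was 0.96 to 0.97, against 0.97 for baseline adjustment alone and 1.12 for complete cases. True, but the reason to impute is to keep the full comparison if PCP practice variation is to be modelled at all.

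The reminders, phone call and payment may well raise response. They do not say how to analyse what remains missing.

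A reader might infer that the planned PedsQL tests at 0.008 would lose substantial power. The documents do not support this: as written, those models contain no PCP covariates and do not depend on PCP reply. A reader might also infer that the secondary results would be biased. That needs reply to differ by arm and to be related to outcome, and nothing in the documents shows either.

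**Conclusion.** The point holds as a minor one. The plan seeks precision from four covariates whose presence depends on a post-randomisation survey reply, and it says neither which secondary models use them nor what happens when they are missing. Under complete-case fitting, adjusted adherence or PedsQL models would be less precise than the unadjusted analysis unless the covariates explained about 33%, 23% or 13% of outcome variance at 70%, 80% or 90% response. At R2 of 0.10 the SE penalty is about 16%, 8% and 1%, against a best possible gain of about 4% if every PCP replied. These sizes rest on assumed r, R2 and complete-case fitting. Selection bias is possible, not shown. The primary analysis does not condition on PCP characteristics and is not affected.

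**What to change.** In the Data Analysis Plan:

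1. Name the secondary models that are to be covariate-adjusted.
2. Adjust the caregiver-reported ones for travel time, insurance and patient age, with baseline PedsQL handled by the shared-baseline model already planned. All are collected from everyone before randomisation; age follows from the child's or dependent's details in the Baseline Assessment, which include "date of birth, race/ethnicity (NIH standardized format").
3. Treat any model with the four PCP covariates as supportive. Fit it on all randomised participants with an observed outcome, for example by multiple imputation with arm, outcome and baseline variables in the imputation model.
4. Show a complete-case fit, if at all, only as a sensitivity analysis, and report PCP response by arm.

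The cost is a few sentences and modest programming, with no new data. The baseline adjusters do not themselves describe PCP practices, so that aim is served by the supportive model. If PCP response is about 90% or higher, a small precision gain is given up in the main secondary result.

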**PARTNERS HUMAN RESEARCH COMMITTEE
PROTOCOL SUMMARY**

Answer all questions accurately and completely in order to provide the PHRC with the relevant information to assess the risk-benefit ratio for the study. Do not leave sections blank.

PRINCIPAL/OVERALL INVESTIGATOR

[name]., M.P.P.

PROTOCOL TITLE

Down Syndrome Clinic to You (DSC2U)

FUNDING

PATIENT-CENTERED OUTCOMES RESEARCH INSTITUTE

VERSION DATE

February 28, 2017

SPECIFIC AIMS

Concisely state the objectives of the study and the hypothesis being tested.

Our core objective is to leverage an innovative technology from Massachusetts General Hospital (MGH), which engages parents/caregivers, so that we can begin to reduce specific health care disparities experienced by those underserved patients with Down syndrome (DS). Specifically, through a randomized control trial (RCT), we will test whether patient/caregiver-initiated online reports with personalized recommendations versus usual care will increase caregiver-reported, provider-driven health actions consistent with national DS guidelines. While all patients with DS have a disparity as defined by their disability, we also intend to mitigate the compounding disparities of geographic location, race/ethnicity, and socioeconomic factors for the majority of families and overcome the limited reach of DS specialty care by taking advantage of the broader reach of the Internet.

BACKGROUND AND SIGNIFICANCE

Provide a brief paragraph summarizing prior experience important for understanding the proposed study and procedures.

Down syndrome (DS) is a rare, chronically debilitating genetic condition caused by extra genetic material from chromosome 21. Patients with DS are prone to multiple chronic conditions over their lifetime, including congenital heart disease, thyroid conditions, gastrointestinal disorders, leukemia, obstructive sleep apnea, and accelerated aging, among others. Most patients with DS have their medical care managed by their primary care providers (PCPs), but a recent study showed that <10% of children and adolescents with DS are up-to-date on even the basic recommendations, such as thyroid screens, celiac testing, audiograms, eye exams, and sleep apnea testing.

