After submission of the Baseline Assessment, the parents/caregivers will be e-mailed a unique link to their DSC2U intervention form. The parent/caregiver will need to enter the month and day of birth of the person with Down syndrome to access their form. Using that information and their unique link, they can return to and complete the DSC2U form (Appendix H) at their convenience. Reminder e-mails to complete the DSC2U form will be sent at 4, 3, and 2 weeks prior to their son's/daughter's scheduled PCP annual well visit appointment. After they have completed DSC2U form, the system will send the parent/caregiver a link to their Caregiver Checklist (Appendix I) and Primary Care Provider Plan (Appendix J), which they will access by entering the month and day of birth of the person with Down syndrome. The DSC2U Caregiver Checklist and Primary Care Provider Plan will be accessible online until the end of the study period and may be downloaded and printed at the user's discretion.

Control Arm

After submission of the Baseline Assessment, parents/caregivers in the Control arm will be sent an e-mail message thanking them for their participation in the study. Included will be a reminder to let study personnel know if their son's/daughter's scheduled appointment with the PCP changes. Control arm participants will be receiving usual care—that is, the natural advice and recommendations that would be offered by their PCPs. (Upon conclusion of the RCT, control group participants will be offered the same Caregiver Checklist and Primary Care Provider Plan intervention.)

PCP Visit

Prior to each patient's scheduled PCP visit, the parent/caregiver will receive 2 reminders for their upcoming appointment, including a request to let our study personnel know if the date of the appointment has changed. Because the timing between study enrollment and scheduled PCP visit will vary among participants, we will plan to send these appointment reminders at approximately 4 weeks, then 1 week prior to the scheduled appointment.

Post-Visit Assessments (Both Intervention and Control Arms)

- Secondary outcome measures: PedsQL 2.0 Family Impact Module; PedsQL 4.0 parent-proxy, standard Short Form 15 Generic Core Scales (Appendix G)

In addition, with direct input from our Patient/Caregiver working group (WG) and PCP WG, we will be designing three novel surveys:

- Health Care Outcome Survey (for parents/caregivers) (for Primary Outcomes) (Appendix F)

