- Parent/Caregiver Experience Survey (for Secondary Outcomes) (Appendix K)
- Primary Care Provider Experience Survey (for Secondary Outcomes) (Appendix L)

Survey Implementation

The Experience Surveys (for both the parents/caregivers and PCPs) will be administered approximately 2 weeks after the PCP visit at Post-visit Assessment 1 (T1) (Figure 1). Parents/Caregivers will be invited by e-mail to complete their experience survey through REDCap. PCPs will receive their experience survey by mail, with an option to complete the survey electronically on REDCap. PCPs whose e-mails were provided by the parents/caregivers will also receive a direct invitation by e-mail to complete their survey. In order to minimize loss to follow-up, reminder e-mails will be sent 3 times about 2 weeks apart, concluding with a phone call in the eighth week by our study personnel. We certainly hope to maximize the PCP response rate, but our primary outcomes are not dependent on their responses.

Parents/Caregivers will be asked by e-mail to complete the Health Care Outcomes Survey through REDCap approximately seven months after the PCP visit at Post-visit Assessment 2 (T2) (Figure 1). In order to minimize loss to follow-up, reminder e-mails will be sent 3 times about every 2 weeks apart, concluding with a phone call in the 8th week by our study personnel.

[figure not shown]

Figure 1. Survey implementation at various points.

- **Baseline:** Health Care Outcome Survey, PedsQL 2.0 Family Impact Module and PedsQL 4.0 parent-proxy, standard Short Form 15 Generic Core Scales
- **T₀ (PCP Visit)**
- **T₁ (Post-visit Assessment 1):** PedsQL 2.0 Family Impact Module and PedsQL 4.0 parent-proxy, standard Short Form 15 Generic Core Scales, Parent/Caregiver Experience Survey, and PCP Experience Survey
- **T₂ (Post-visit Assessment 2):** Health Care Outcome Survey, PedsQL 2.0 Family Impact Module and PedsQL 4.0 parent-proxy, standard Short Form 15 Generic Core Scales

Validation Assessment

Ten percent of the respondents across both groups will be asked to validate their self-report by providing documentation of laboratory and procedural results. For example, if parents attest to thyroid checks being done for their

sons/daughters, they will be asked to send documentation of the primary outcomes (e.g. study report or physician sign off). These participants will also receive 3 reminder e-mails and a phone call every 2 weeks.

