If discrepancies are identified between parental report and source verification in more than 10% of these samples, then our team will perform a full verification of all 200 participants. Verification will be made by source documentation (e.g., sleep study reports) or verbal confirmation through telephone calls to primary care physicians.

Primary Outcomes:

We will be measuring adherence to detect improvement in: thyroid screening, celiac disease screening, sleep apnea testing, ophthalmology exams, and audiograms

- *Thyroid*: TSH should be checked annually beginning at age 1
- *Celiac disease*: if symptoms present, obtain tTG-IgA and total IgA annually
- *Sleep study*: performed by 4 years of age and, again, if symptomatic
- *Ophthalmology exam*: annually, ages 1-5; every 2 years, ages 5-13; every 3 years, ages 13-21; every 2 years, ages 21 and older
- *Audiograms*: annually up to age 21, every 2 years thereafter

The indication for 1, 2, 3, 4, or 5 evaluations for a given participant at the time of their PCP visit based on age, history, and symptoms will be collected prior to randomization as described in the "Baseline Assessment" section.

Secondary Outcomes:

We also want to determine whether the intervention improves quality of life as measured by the nationally validated PedsQL survey instruments.

Six summary scores will be derived from the two PedsQL instruments: measures of (1) psychosocial health, (2) physical health, and (3) an overall total score from the PedsQL 4.0 parent-proxy, standard Short Form 15 Generic Core Scales; and measures of (4) parental health-related quality of life, (5) family functioning, and an (6) overall total score from the PedsQL 2.0 Family Impact Module.

We will also measure the quality of experience with the intervention from parents and PCPs and identify ways that the *Caregiver Checklist* and *Primary Care Provider Plan* could best serve the needs of underserved patients with DS. For this assessment, rather than assuming we know which questions to ask to best assess their experience, we will engage our Parent/Caregiver and PCP WGs to help us pose relevant questions. Our expectation is that the assessments will ask for their level of satisfaction with the content and

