guidance offered by the *Caregiver Checklist* and *Primary Care Provider Plan*, similar to the voluntary questionnaire used in our preliminary study described above. We also anticipate including open-text responses solicited from caregivers and providers about their experience using the system.

Data Analysis Plan

Our primary analysis will compare the mean number of caregiver-reported evaluations completed within 7 months of the index PCP visit between the intervention and usual care arms. We will analyze the data using a generalized linear model assuming beta-binomial distributed counts of evaluations among those indicated with parameters estimated by maximum likelihood. We will confirm our inference using a permutation test by direct randomization of assigned treatment labels. Significant benefit will be declared if the mean number of recommended tests is greater among participants randomized to the intervention and a two-tailed p-value for the treatment comparison is less than 0.05. A significant effect of the intervention will be declared only if the permutation test concurs with inference from the beta-binomial regression as the permutation test makes no assumptions concerning the true distribution of the data. We will analyze longitudinal changes in our secondary outcome measures using a shared-baseline repeated-measures ANOVA for each of 6 quality of life outcomes derived from the two PedsQL instruments. Linear contrasts will be used to test for treatment-specific improvements over time. As a sensitivity analysis, we will also use simple two-group Wilcoxon ranksum tests to compare changes from baseline in each follow-up assessment individually. With 6 secondary outcomes, we will test each secondary outcome at alpha = 0.008 two-tailed to control for multiple comparisons.

For studies involving treatment or diagnosis, provide information about standard of care at Partners (e.g., BWH, MGH) and indicate how the study procedures differ from standard care. Provide information on available alternative treatments, procedures, or methods of diagnosis.

Not applicable

Describe how risks to subjects are minimized, for example, by using procedures which are consistent with sound research design and which do not unnecessarily expose subjects to risk or by using procedures already being performed on the subject for diagnostic or treatment purposes.

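### Does the plan leave the primary result exposed to caregiver misreporting by not saying how verified data are used and by pooling its validation trigger across arms?

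*Combined protocol and SAP*

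**What the plan says.** The aim in Specific Aims is to test whether the online reports "will increase caregiver-reported, provider-driven health actions consistent with national DS guidelines". The Data Analysis Plan follows: "Our primary analysis will compare the mean number of caregiver-reported evaluations completed within 7 months of the index PCP visit", by beta-binomial regression confirmed by a permutation test, at a two-tailed 0.05.

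Under Intervention Arm, once the form is completed, "the system will send the parent/caregiver a link to their Caregiver Checklist". The Control Arm section gives controls a thank-you message and offers the checklist only after the trial, so the two groups report from different knowledge.

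Validation Assessment sets up the check: "Ten percent of the respondents across both groups will be asked to validate their self-report". Its one illustration begins "if parents attest to thyroid checks being done for their" sons or daughters. Three reminder e-mails and a phone call follow. Full verification starts if discrepancies appear "in more than 10% of these samples, then our team will perform a full verification of all 200 participants". On method: "Verification will be made by source documentation (e.g., sleep study reports) or verbal confirmation through telephone calls to primary care physicians".

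No section says how verified data enter the analysis, whether a sample is a person or an evaluation, or how a report that nobody can confirm is coded.

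**The concern.** Reporting is unblinded, and the checklist tells one arm which tests were recommended. Over-reporting in that arm alone would inflate the treatment difference.

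Two features seem to leave this open. First, the analysis text names only caregiver-reported counts. Read literally, the trial could find its reports unreliable, verify everyone, and still analyse the unreliable reports; or the data source could be chosen after both results are known. Second, the trigger responds to the overall discrepancy rate, so a passed check says little about error confined to one arm. Smaller gaps add to this: the count needed depends on how many respond, the only example concerns tests reported as done, and documents that never arrive have no stated coding.

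At stake would be a false claim of benefit on the primary endpoint.

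**Working it through.** The plan gives no power, SD or error rate for this check, so there is no figure of its own to reproduce.

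**Inputs from the documents.** 200 participants randomised 1:1 (100 per arm); 10% validated; trigger above 10%; two-tailed 0.05.

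**Assumptions.** A sample is a respondent; equal numbers are checked per arm; each discrepant caregiver over-reports one evaluation; no true effect; SD of the evaluation count 1.0 or 1.5. Error rates are illustrative and written intervention v control.

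**Step 1, the count.** 0.10 × 200 = 20 respondents. More than 10% of 20 is more than 2, so at least 3. With 18 or 19 respondents, 2 suffice (2/18 = 11.1%, 2/19 = 10.5%).

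**Step 2, what the trigger detects.** P(X1 + X0 ≥ k), with X1 ~ Bin(n, p1), X0 ~ Bin(n, p0) and n checked per arm. At 20% v 0% and n = 10 this is 1 − (0.1074 + 0.2684 + 0.3020) = 0.322.

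| Error rates | 20 checked, k = 3 | 18 checked, k = 2 | Shift in mean difference |
|---|---|---|---|
| 10% v 10% | 0.323 | 0.550 | 0 |
| 15% v 5% | 0.323 | 0.553 | 0.10 |
| 20% v 0% | 0.322 | 0.564 | 0.20 |

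The trigger is indeed nearly blind to the difference between arms.

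**Step 3, false benefit on caregiver report.** 1 − Φ(1.96 − d/SE), with SE = SD × √(2/100), which is 0.141 or 0.212. For d = 0, 0.10 and 0.20: 2.5%, 10.5% and 29.3% at SD 1.0; 2.5%, 6.8% and 15.5% at SD 1.5.

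**Step 4, the part that the use of verified data governs.** The 29.3% mixes trials that pass the check with trials that fail it. Saying how verified data are used matters only in the second group. At 20% v 0%, SD 1.0 and 20 checked, treating check and test as independent:

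- fired: 0.2926 × 0.3222 = 0.094
- passed: 0.2926 × 0.6778 = 0.198

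A simulation that draws the checked respondents from the arm itself and carries the variance added by over-reporting gives:

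| | 20 checked, SD 1.0 | 20 checked, SD 1.5 | 18 checked, SD 1.0 | 18 checked, SD 1.5 |
|---|---|---|---|---|
| False claim, check fired | 0.099 | 0.053 | 0.166 | 0.089 |
| False claim, check passed | 0.174 | 0.097 | 0.109 | 0.061 |

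The total at SD 1.0 and 20 checked is 0.099 + 0.174 = 0.273, slightly below the 0.293 of step 3.

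**Step 5, whether an arm-specific check would do better.**

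- A Fisher exact test of 10 v 10 needs at least 5 v 0 discrepancies when controls have none. Power is P(Bin(10, 0.2) ≥ 5) = 0.033 at 20% v 0%, 0.150 at 30% v 0% and 0.367 at 40% v 0%.
- A trigger of 2 of 10 in either arm fires 0.624 of the time at 20% v 0%, against 0.322 for 3 of 20 pooled. But 2 of 20 pooled also gives 0.624, so the gain comes from the lower count.
- Lower counts cost false alarms. At 5% v 5%, full verification starts with probability 0.075 (3 of 20 pooled), 0.165 (2 of 10 in either arm) or 0.264 (2 of 20 pooled).
- With 18 checked, the existing rule equals a 9-per-arm split at 20% v 0% (both 0.564) and detects more at 20% v 5% (0.685 v 0.595).

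**Step 6, the text on verified data.** Validation Assessment commits the team to checking everyone once a numerical threshold is crossed. The Data Analysis Plan is silent about the product of that work. Nothing says verified data will be set aside, so the two sections do not contradict each other.

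**The case for a change.** The strongest reply is that likely intent is not pre-specification. Verified and reported counts could fall on opposite sides of 0.05, and the text does not name the one that counts. Verification of 200 families will also be incomplete, so even a team set on using verified data needs a coding rule.

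The omission stands as a fact. It weighs less than it appears to. The event that starts full verification is a discrepancy threshold set in advance, not the treatment result. An analyst holding a complete set of verified outcomes, obtained because the reports had failed a check, would make them primary and show caregiver report beside them.

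A written rule for unconfirmable reports brings no clear gain either. The obvious one, keeping the caregiver's word, could retain the very over-reports at issue, because a test that was never done leaves no document. Whether a source contradicts the report or is merely silent is something analysts would have to judge under any rule.

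The smaller gaps are partly covered. Non-return is met by reminders and a call, and the methods of verification include "verbal confirmation through telephone calls to primary care physicians". The thyroid case is only an example: the general wording compares report with source and favours neither direction. The sample unit remains undefined, and the trigger probabilities depend on it.

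**Conclusion.** No change follows. The use of verified data is missing detail that analysts would fill in the sensible way: an omission, not a contradiction. The pooled trigger is a fair trade-off for a small audit. No sample of this size can test a difference between arms, and full verification, once started, covers both arms and can correct a differential error.

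The risk tied to the missing sentence is a false claim of benefit of about 5% to 17% (0.053 to 0.166), and it arises only if the trigger fires and the verified data are then disregarded. It also rests on 20% v 0% over-reporting of exactly one evaluation, no true effect, SD 1.0 to 1.5, and 18 to 20 respondents as the unit. The larger figure of about 29% is not a measure of this gap: with 20 checked, roughly two thirds of it (0.174/0.273 = 64% in the simulation at SD 1.0) arises when the check passes, which no statement about verified data would alter.
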